## **Methods.**

**Echocardiography.** Repeat echocardiography assessment at Y30 will enable longitudinal assessment of LV and LA structure and function. See Section 5.3. for details. We will use echo-derived measurements, including LVM, LA dimension, tissue Doppler assessment of LV diastolic function, LV myocardial strain (particularly longitudinal strain) by STE, LV geometry, EF/FS, and valvular assessment. Because of the age of the cohort members, CARDIA is well positioned to assess alterations of cardiac function as data from other cohort studies suggest that during the age range of the 50s, metabolic and vascular alterations appear to accelerate leading to the greater frequency of events occurring in the 60s and 70s. The use of speckle tracking analysis will additionally enable unique assessment of longitudinal myocardial function, LA function through LA strain measurements, and LV diastolic function.

**Other variables.** Data collection will include repeated assessments of selected key variables, including sociodemographic, lifestyle/behavioral, and psychosocial factors related to subclinical and clinical outcomes. Data collection is described in detail in subsequent sections. We will employ previously used standardized instruments, including smoking, alcohol intake, physical activity, health-related quality of life, income, employment, education, health care access, discrimination, depression, and self-reported

neighborhood environment characteristics related to physical activity and dietary habits. Through previously-funded ancillary studies, we have geocoded participants' home addresses through Y25 and anticipate ancillary study applications for Y30 geocoding that will provide an additional level of environmental factors such as neighborhood-level socioeconomic conditions, physical activity and nutrition resources, etc. Methods and questionnaires are available on the CARDIA public website: <http://www.cardia.dopm.uab.edu/>

We will obtain anthropometric measures, body weight, height, and hip and waist girth, as done at earlier exams. BP will be measured using the *OmRON* (Omron Corporation; Kyoto, Japan) HEM907XL sphygmomanometer three times after a five-minute seated rest period. Fasting blood will be obtained for assay of lipids, glucose, and creatinine; urine will be obtained for albumin/creatinine excretion. DM and hypertension are defined using a combination of physiologic variables (e.g., standard cutpoints for glucose) and medication use (e.g., DM medications).

**Clinical events.** We will continue to collect and adjudicate clinical events as in Section 5.10.

**Previously-collected data.** In addition to the wealth of environmental, social, behavioral, and biological risk factor data collected over the past 25 years, and described briefly above, we have also collected substantial imaging data on adiposity (dual-energy x-ray absorptiometry) at Y20, abdominal computed tomography (CT) at Y25, and subclinical disease (chest CT [for CAC and pericardial fat] at Y15, Y20, and Y25; carotid ultrasound for IMT at Y20). We will continue current efforts to understand the etiology of racial disparities in these measures and examine the degree to which these measures account for racial differences in clinical events.

**Statistical approach.** Mediation analysis is the fundamental approach to the study of race differences, wherein the unadjusted race difference in an outcome variable is compared to the race difference after adjusting for variables that are thought to explain or mediate the race variable. In this analysis, the statistical predictive power of the added covariates is noted and interpreted for a fuller understanding of other predictors and of the nature of the mediation. In mediation regression analyses dealing with race differences in CVD risk factors (H1), the CVD risk factor level will be the dependent variable, while predictors are as listed in the hypothesis above. Note that smoking will be dealt with both as a risk factor and as a predictor of other risk factors. CARDIA has collected a wide array of variables within each class of predictors. Addressing H2, the dependent variables in the mediation analysis are echo variables with the primary hypothesized mediators, BMI, BP, and insulin resistance, having been measured repeatedly. The proposed Y30 echo provides an opportunity to examine effects of these variables on changes in the race effect at an age (mean 50 years at Y25, mean 55 years at Y30) when acceleration of subclinical cardiac abnormalities is expected. In H3, we hypothesize that the mediation analysis will identify important mediators, including baseline and cumulative levels of BP, and thus help to explain the race effect. H4 will be tested by studying effect modification in models that are similar to the mediation models above. However, the effect modification models will include race x covariate interaction terms. For example, if blacks have greater sensitivity to BP than whites, the black race x BP interaction term will be positive.

**Summary.** We hypothesize “a point of no return,” for example, due to organ damage, will be reached in these hypotheses. We anticipate that a web of connections will be evident among risk factors, lifestyle/habits, socioeconomic position, psychosocial factors, and resources and environment early in the study, which will augment any ancestry or genetic variants that link risk factors. These results will also track (that is, people will tend to retain their ranking as they age). However, adjustment for potential mediators will not affect the race differences equally over time, and a point of no return will be suggested by a change in the mediation effect of potential mediators at a point in time.

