An independent relationship of race with CVD outcomes after adjustment for CVD risk factors could be due to biological, genetic, behavioral, environmental, or other factors. Biological differences may include, for example, differences in atherosclerotic plaque composition. Biological differences in turn could be due to genetic differences between populations, as has been proposed for several CVD outcomes. For example, analyses of ancestry markers (admixture) have concluded that genetic effects may be important in determining CAC and carotid IMT among blacks in MESA. In the HyperGEN Study, a chromosome 11 region containing myosin-binding protein C, mutations of which are linked to familial hypertrophic cardiomyopathy, demonstrated linkage with LV contractility in blacks, while a promoter polymorphism in the GNAQ gene has been associated with decreased survival time in black HF patients. In CARDIA, African ancestry was inversely related to forced expiratory volume in 1 second (FEV1) and forced vital capacity (FVC), relationships that were replicated in the Health, Aging, and Body

Composition (Health ABC) Study and Cardiovascular Health Study (CHS) cohorts. In several cohorts including CARDIA, the presence of sickle cell trait was associated with an increased risk of chronic kidney disease (CKD), decline in eGFR, and albuminuria compared with non-carriers, suggesting an association with the higher risk of kidney disease in blacks. While the physiologic effects of genetic risk factors on racial disparities in health are still poorly understood, there is some evidence that genetic information can be successfully incorporated into disparity research to reduce measurement and selection bias.

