Black-white differences in subclinical disease seen to date in CARDIA, with the greatest prevalence of CAC in white men and little difference among women, do not mirror the racial disparities in clinical events noted in national mortality data. With the notable exception of MI, there is a large preponderance in blacks of the hypertension-related clinical outcomes, including HF, ESRD, and stroke. These mirror the greater onset in blacks of early-onset CKD, albuminuria, and lower small artery elasticity in blacks. Through Y20, cases of clinical HF occurred almost exclusively in blacks. The risk factors at Y0 for HF, listed in Section 5.1, included higher diastolic BP. Most of the participants with hypertension at Y0 were not being treated.

As described in Section 5.1.2., CARDIA has shown the importance of long-term exposure to risk factors. The time-averaged cumulative exposures to non-optimal lipid levels between age 20 and 35 years was significantly related to CAC prevalence at Y20^34, and the association was similar across race and sex, and strongly graded. There was a graded association between Y20 CAC prevalence and exposure to “pre-hypertension” before age 35, especially systolic pre-hypertension. Nearly 20% of the cohort developed pre-hypertension before age 35, with greater odds in black, male, overweight, and lower annual income and education participants.

**Hypotheses.** We list four hypotheses related to racial disparities in the development of, exposure and susceptibility to CVD risk factors as they related to disparities in subclinical and early clinical events:

1. Racial differences in CVD risk factor levels are partially but not fully explained by lifestyle/habits (physical activity, diet, smoking), socioeconomic position, psychosocial factors, and resources and environment at Y0 and their trajectories over 30 years, as well as by ancestry and genetic variants.
2. Greater baseline and cumulative levels of BMI, BP, and insulin resistance in blacks than in whites are the primary factors associated with greater increases in blacks of LVM, LV systolic strain defined by speckle tracking, and diastolic dysfunction defined by tissue Doppler over 25 years from the Y5 to the Y30 CARDIA Examination, and during the 5-year period from Y25 to Y30.

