3. Greater Y0 and cumulative levels of several CVD risk factors (BP, smoking, lipids), lower levels of physical activity, and higher incidence of hypertension and DM in blacks than in whites partially, but do not fully, explain the higher cumulative incidence of early clinical events in blacks than in whites over 30 years and during the 5-year period from Y25 to Y30.
4. Blacks have a greater sensitivity than whites to any given level of BP for hypertension-related outcomes including HF, stroke, and subclinical LV dysfunction.

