 Ponderal index is computed as weight (in kg)/ht (in meters).

measure of central adiposity that correlates well with visceral fat. Among nearly 400 CARDIA participants who participated in an ancillary study in which visceral fat was measured, the correlation of waist circumference with visceral fat is 0.44 for black men, 0.64 for white men, 0.62 for black women, and 0.66 for white women.

3. **Hip Circumference**—Hip circumference was measured during the first five CARDIA exam cycles (through Y10) but was not assessed at the Y15 and Y20 Exams. Hip circumference was measured in Y25 and is included again in the Y30 Exam because of data showing the association of waist-hip ratio (WHR) with cardiovascular risk and the value of ratios such as WHR in adjusting for ethnic differences in body shape.

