#### Functions and Responsibilities

- Prepare the protocol and exam MOO with the cooperation of the Steering Committee.
- Prepare and implement a system for data collection, transmittal, logging, editing, management, extraction, and analysis.
- Work with the investigators in the development, pretesting, construction of forms, and associated procedures.
  - Obtain inter- and intra-observer reliability measurements.
  - Obtain reliability for all questionnaires and procedures used in the study so that such information might be incorporated into the analyses.
    - Manage subcontracts for central laboratories as requested by NHLBI.
    - Monitor QC of external laboratories.
    - Interact with the Clinic Coordinators and Principal Investigators to orchestrate the training sessions and staff certification for the Y30 Exam.
    - Produce minutes of the Steering Committee meetings and conference calls.
    - Assist in the organization and conduct of site visits to each center to ensure compliance with the provisions of the exam MOO.
    - Monitor the completeness and accuracy of submitted data forms. Notify field centers and the relevant study units of error rates and/or deficiencies in forms submitted.
    - Design and implement a distributed data analysis system.
    - Notify the Principal Investigator if any specific local problems arise in the field center's performance. Notify Project Officer if timely resolution is not possible.
    - Issue periodic reports to NHLBI, the Steering Committee, and the OSMB. Specific reports will include predefined QC monitoring reports.
    - Develop new or modify existing statistical methods for data analyses.
    - Facilitate the preparation of study publications in cooperation with other investigators and according to the publications policies.
    - Take the lead on specific manuscripts depending on investigator interest and in accordance with the publications policies.
    - Lead efforts to periodically review and revise the publications policies.

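### A race difference left after adjustment cannot by itself show that H1 or H3 of Objective 3 is right, because error in the mediators leaves one too

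*Protocol*

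**What the plan says.** Protocol Section 5.1.3, Statistical approach, makes mediation analysis the basic method for race differences: "the unadjusted race difference in an outcome variable is compared to the race difference after adjusting for variables" that are thought to explain or mediate them. Two of the four hypotheses predict an intermediate result.

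- H1: "Racial differences in CVD risk factor levels are partially but not fully explained by lifestyle/habits", socioeconomic position, psychosocial factors and environment, at Year 0 and as 30-year trajectories, and also by ancestry and genetic variants.
- H3: Year 0 and cumulative risk factor levels, physical activity, and incident hypertension and diabetes "partially, but do not fully, explain the higher cumulative incidence of early clinical events in blacks than in whites".

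The rationale in the same section says how a remaining race effect may be read: "An independent relationship of race with CVD outcomes after adjustment for CVD risk factors could be due to biological, genetic, behavioral, environmental, or other factors". Error in the mediators is not named there. The section gives no measurement-error step and no numerical criterion for incomplete explanation.

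Two statements bear on the point from the other side. The H2 mediators are described as "having been measured repeatedly". Section 8.3 gives the coordinating center the duty to "Obtain reliability for all questionnaires and procedures used in the study so that such information might be incorporated into the analyses", without tying this to the mediation models.

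**The concern.** The result that H1 and H3 predict is a race coefficient that shrinks on adjustment but stays away from zero. An error-prone mediator tends to produce the same pattern when mediation is complete. The hypothesis and its main rival then give the same finding.

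Error differs by mediator. In Table 1 the diet history was taken only at Years 0, 7 and 20, and discrimination only at Years 7, 15, 25 and 30. Physical activity was asked at every exam, but by a brief self-report (Section 5.12). The Year 0 levels named in both hypotheses are single-exam values. Resting blood pressure, lipids and tobacco use have nine exams, so their cumulative levels carry less random error.

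Objective 3 is meant to find the basis of the disparities. A residual produced by measurement error could be taken as evidence of causes outside the measured set.

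**Working it through.** The protocol gives no effect size, alpha or power for H1 to H4, so there is no figure to reproduce.

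**Inputs from the protocol.** N = 3,445 at Year 30 and 51.5% black at enrolment (Section 4.1); 272 CVD endpoints as of January 2015 (Section 2).

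**Assumptions.** Two-sided 5% test; one mediator with within-race SD 1; race gap D in the mediator; slope b on an outcome with within-race SD 1; no direct race effect; random error that does not depend on race or outcome; within-race reliability λ.

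**Step 1, bias.** The unadjusted gap is bD. The expected race coefficient after adjusting for the error-prone mediator is (1 − λ)·bD, so the share left is 1 − λ and the apparent share explained is λ, although the true share is 100%.

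**Step 2, chance of a significant residual.** With q = 0.515 × 0.485 = 0.2498 and ρ² = D²q/(D²q + 1/λ), SE = √[(1 − b²λ)/(N·q·(1 − ρ²))].

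Example with D = 0.5, b = 0.5, λ = 0.7: residual 0.3 × 0.25 = 0.075; ρ² = 0.0624/(0.0624 + 1.4286) = 0.042; SE = √(0.825/824.5) = 0.0316; z = 2.37; probability Φ(2.37 − 1.96) = 66%. Simulation of the same setting also gave 66%.

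| Assumed setting | λ = 1.0 | 0.9 | 0.8 | 0.7 | 0.5 |
|---|---|---|---|---|---|
| D = 0.3, b = 0.3 (outcome gap 0.09 SD) | 5% | 6% | 8% | 13% | 27% |
| D = 0.5, b = 0.5 (gap 0.25 SD) | 5% | 13% | 36% | 66% | 97% |
| D = 0.55, b = 0.55 (gap 0.3 SD, within-race R² 0.30) | 5% | 17% | 50% | 83% | 100% |
| D = 0.73, b = 0.55 (gap 0.4 SD, within-race R² 0.30) | 5% | 25% | 73% | 97% | 100% |

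Simulations of these settings agree to within about two percentage points.

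**Step 3, events (H3).** Taking the residual hazard ratio as roughly HR^(1 − λ), with 272 events and an assumed crude HR of 2.0, it is 1.07, 1.15, 1.23, 1.32 and 1.41 for λ = 0.9, 0.8, 0.7, 0.6 and 0.5. By Schoenfeld's formula it is significant 8%, 21%, 40%, 63% and 82% of the time. At a crude HR of 1.5 the range is 5% to 39%; at 2.5, 11% to 97%.

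**Step 4, averaging.** Over k exams with independent errors, λ becomes kλ/(1 + (k − 1)λ). From 0.6 at one exam it becomes 0.82 with three and 0.93 with nine, leaving 18% or 7% of the gap instead of 40%. Systematic self-report error is not averaged away.

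**Step 5, sign.** With several mediators uncorrelated within race, the residual is Σ(1 − λⱼ)bⱼDⱼ. Take mediator 1 with λ = 0.95, b = 0.5, D = 0.5 and mediator 2 with λ = 0.5, b = 0.4, D = −0.3. The gap is 0.25 − 0.12 = +0.13 and the residual 0.0125 − 0.06 = −0.05. A simulated case, in which a poorly measured mediator had no race gap of its own but correlated 0.6 with the other, left −0.06 against a gap of +0.15. Table 3 shows one opposing gap: dyslipidemia in 36% of black men and 46% of white men.

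**Step 6, can it be corrected?** With D = b = 0.5 and a known λ of 0.6, regression calibration brought the residual to 0.000 and the false-positive rate to 5.4%, from 87.5% uncorrected.

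**The case against.** The strongest reply is that the protocol has no rule that turns a non-zero residual into a conclusion. The race differences are compared and the covariates interpreted, and for H3 the stated aim is to identify mediators. That is correct: the reading is inferred from the wording of H1 and H3 together with the method. What stands is that this comparison is the only stated means of assessing them.

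Second, correction for measurement error may be in an analysis plan not seen here, and Section 8.3 leaves room for it. That limits the point to a modest addition. An optional use of reliability, not linked to these models, does not settle it.

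Third, the mediators are better measured than a short list of the weak ones suggests. This largely stands for H3, whose blood pressure, lipids, smoking and activity were recorded at all nine exams. For H1, activity and tobacco also have nine exams, and the dietary practices form has six. It does not cover diet history, discrimination or single Year 0 values.

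Three stronger readings are tempting, and the protocol does not support them.

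- A reader might infer that the residual must lie above zero. Step 5 shows that it can reverse.
- A reader might infer that it will be put down to ancestry or biology. Ancestry and genetic variants are in the H1 adjustment set, the rationale lists behavioral, environmental and other causes too, and it names unrecorded earlier exposure as a source of confounding.
- A reader might infer that the high false-positive rates apply across the board. They need sizeable gaps and low reliability; the first row of the table stays at 6% to 27% for reliability 0.9 to 0.5.

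**Conclusion.** The point holds in a limited form. Under complete mediation, error in the mediators biases the adjusted race coefficient away from zero, usually toward the observed gap. A non-zero residual alone therefore cannot tell incomplete explanation from complete explanation with imperfect measurement.

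For one mediator the share left is 1 − λ: 10% at reliability 0.9 and 50% at 0.5. False significant residuals run from about 5% to 100% over that range.

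These figures rest on assumed gaps, slopes and reliabilities and on random error equal across races; the protocol gives reliabilities for few of these measures. As an indication that proxy quality can vary by race, Section 5.5 reports that "the correlation of waist circumference with visceral fat is 0.44 for black men, 0.64 for white men". Waist is not a named H1 or H3 mediator, so this is not used in the calculation. The point is a worthwhile, inexpensive improvement and does not invalidate the mediation analysis.

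**What to change.** Add to Section 5.1.3, Statistical approach:

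- The explained share and the residual race effect will be reported with confidence intervals, uncorrected and over a stated reliability range for each mediator.
- Reliabilities will come from the data to be obtained under Section 8.3 and from same-visit or quality-control duplicates, such as the repeated blood pressure readings (Section 5.4) and the duplicate anthropometry and blind laboratory samples (Section 6.4). These miss day-to-day variation and systematic self-report error, so the range should extend below them. Where no reliability is available, the range is stated as an assumption.
- Exams years apart will not serve as replicates, because true change would count as error. For example, a Year 0 mediator measured perfectly, truly explaining 50% and tracking at 0.5 between exams, would have its slope doubled and would appear to explain 100%.
- The reliability at which the residual would vanish will be given. With one mediator this equals the uncorrected share explained, so an apparent 70% becomes 100% at reliability 0.70.
- Incomplete explanation will be claimed only if the residual excludes zero across the plausible range.

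The cost is extra analysis of data already held or planned, wider intervals, and fewer claims that a gap is not fully explained.

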Similar findings were observed for subclinical disease measures in CARDIA. Loria et al. reported that while Y15 risk factor levels (e.g., BP and LDL-cholesterol) are significantly associated with Y15 CAC, these relationships disappear with an adjustment for baseline (Y0) risk factor levels. Conversely, the Y0 risk factor levels measured in young adulthood, although low, are significantly related to Y15 CAC with or without adjustment for the Y15 levels. Baseline risk factor levels also predicted CAC equally as well as averaged 15-year levels. CARDIA Y25 data confirmed these findings. Furthermore, Pletcher et al. demonstrated that pre-hypertension prior to 35 years of age is strongly associated with CAC later in life. Similar findings were also observed for non-optimal lipid profiles. These results demonstrated that higher risk factor levels in young adulthood, although not clinically high, may impact the development of subclinical CVD years later.

**Hypotheses.** It remains unclear why remote measurements are more predictive of CVD events than current assessments. One explanation is that risk factor levels at young ages may more appropriately reflect long-term exposure to elevated risk factor levels while medical or lifestyle interventions may have altered risk factor measurements obtained closer to events. Long-term exposure to elevated risk factor levels may cause irreversible end-organ damage. Risk factors (e.g., BP and cholesterol) may subsequently be lowered by medication to ideal levels, but the risk of CVD may still be higher than in those who have always had ideal risk factor levels. It is also possible that young adulthood is a more vulnerable period—when exposure to higher risk factor levels may be more likely to lead to end-organ

damage. These issues have never been clearly addressed and require sophisticated statistical and epidemiologic approaches, as well as specialized data resources. The risk factor data, echocardiography data, other subclinical data, and clinical CVD data collected during the 30 years of follow-up in CARDIA offer a unique opportunity to assess the impacts of the timing and levels of risk factors on cardiac function and subclinical and clinical CVD.

We list three hypotheses, illustrative of the many hypotheses that can be generated to approach this objective.

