1. Cumulative levels of risk factors (e.g., BP, lipids, number of cigarettes, fasting glucose, and BMI) are associated with the occurrence and progression of subclinical atherosclerosis, myocardial dysfunction, and early CVD events, independent of medications and other relevant covariates (e.g., age, sex, race, education, and income).
2. Exposure to elevated risk factors during young adulthood is associated with the occurrence and progression of subclinical atherosclerosis, myocardial dysfunction, and with early cardiovascular events. The relationships are stronger than, and are independent of, the relationships between the concurrent risk factor levels and the above outcome variables.
3. After a risk factor for a subclinical or clinical disease endpoint has been abnormally high for a sufficient period, complete reversibility is lost, in that reduction of the risk factor level does not reduce the risk to that associated with persistently normal levels. Figuratively, “a point of no return,” for example due to organ damage, will be reached.

**Methods.** Several general methods will be used. The outcome variables include continuous variables (e.g., LVM index [LVM [gm]/height [m]2.7], end systolic volume, end diastolic volume, myocardial strain, EF, and estimated glomerular filtration rate (eGFR)), ordinal and dichotomized variables (e.g., diastolic dysfunction, left ventricular hypertrophy (LVH), and CAC), and failure time (HF, CHD, and CVD events). We will rely heavily on cross-tabulations, frequency counts, and standard regression methods, particularly Cox proportional hazards regression models and consideration of prediction from predictors measured at different examinations or combinations of examinations. In this section we propose several innovative statistical methods, providing some examples to illustrate the ideas. The methods apply to continuous outcomes (e.g., LVM index) using the identity link function, as well as other types of outcomes using nonlinear link functions, such as logistic regression.

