**1. Cumulative exposure to each risk factor over 30 years of follow-up.** We will estimate the cumulative exposure to each risk factor during the 30 years of follow-up by calculating the “area under the exposure curve” of the risk factor levels measured nine times during the 30 years. The missing values will be imputed using the multiple imputation method based on a mixed effect regression model with all the information collected over time. The relationship between the cumulative exposure to each risk factor and the outcome variable will be analyzed using spline regression, adjusting for other relevant risk factors. The main purpose of this approach is to see whether there is a threshold of cumulative exposure to the risk factor beyond which the impact of the exposure to the risk factor on the outcome will be accelerated.

**2. Cumulative exposure during different time periods.** In this approach, we will divide the 30-year period of follow-up into three distinct 10-year time periods (Y0 to Y10, Y10 to Y20, and Y20 to Y30). For each period, we will calculate the cumulative exposure to each risk factor during that period. The relationship between the cumulative exposure during each period and the outcome of interest, adjusting for other risk factors, will be examined. In the final analysis, we will enter all three cumulative exposures (over the three periods) in the same model to assess the relative importance of the exposure to the risk factor during the different time periods. The results will help to understand the impact of the

risk factor exposures during different time periods on the outcome of interest. Since the cumulative exposure in each period is adjusted for the cumulative exposures in the other periods, we will note whether a given period is more vulnerable than others. We may repeat the analyses using different time periods (e.g., six 5-year time periods).

**3. Nonparametric/Semiparametric Extensions.** We will conduct semiparametric or nonparametric analysis to characterize the detailed dynamic effect of the time-dependent risk factors acquired throughout young adulthood and middle age on the various outcomes of interest. For continuous outcome  $Y$ , we will employ the varying coefficient model:

$$Y = \beta_0(t) + \beta_1(t)X(t) + \varepsilon \quad \text{or} \quad Y = \beta_0(t) + \int_0^t X(u)du \times \beta_1(t) + \varepsilon,$$

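### A change over time in the mediated share of the race gap does not measure the lost reversibility that defines the point of no return, and no Objective 2 model is assigned to test it

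*Protocol*

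**What the plan says.** Section 5.1.2 (Scientific Objective 2), Hypothesis 3, defines the point of no return: after a long enough abnormal exposure, "complete reversibility is lost, in that reduction of the risk factor level does not reduce the risk to that associated with persistently normal levels". The hypotheses there are introduced as examples: "We list three hypotheses, illustrative of the many hypotheses that can be generated to approach this objective".

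The Methods of Section 5.1.2 then offer several approaches:

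- Method 1 fits a spline on 30-year cumulative exposure and asks "whether there is a threshold of cumulative exposure to the risk factor beyond which the impact of the exposure" accelerates.
- Method 2 splits follow-up into Y0–Y10, Y10–Y20 and Y20–Y30, and "we will enter all three cumulative exposures (over the three periods) in the same model". Its stated use is to judge whether one period is more vulnerable than the others.
- Method 4 includes a third hazard model, in which exposure at each earlier time carries its own weight.

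None of these is named as the test of Hypothesis 3.

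Section 5.1.3 (Scientific Objective 3), Statistical approach, describes mediation analysis as one in which "the unadjusted race difference in an outcome variable is compared to the race difference after adjusting for variables" thought to explain it. The Summary of that section takes up the point of no return again, with organ damage again as the example, and says that "a point of no return will be suggested by a change in the mediation effect of potential mediators at a point in time".

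**The concern.** One term is attached to two different quantities. In Section 5.1.2 it is a contrast between exposure histories: high and then lowered, against never high. In Section 5.1.3 it is read from a shift over calendar time in how far covariates shrink a black–white difference. People whose risk factor came down are not compared with anyone in that second quantity.

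An analyst following the Section 5.1.3 Summary could therefore report evidence of irreversible damage at a given age when only the race gap in a risk factor, or in something unmeasured, had changed. The analyst could also miss irreversible damage that affects both groups alike. The Section 5.1.2 Summary hopes to identify critical points for intervention, so a misplaced point of no return would bear directly on what the study concludes about prevention.

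**Working it through.** The protocol gives no figure here, so there is nothing to reproduce. The check compares the two quantities and then looks at what the Objective 2 models can deliver. All numerical inputs below are assumptions chosen to show the logic. They are not estimates for this cohort.

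**1. The two quantities**

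- Reversibility (Section 5.1.2, Hypothesis 3): Δ = mean outcome in people with high earlier and normal later exposure, minus mean outcome in people normal throughout. Full reversibility means Δ = 0.
- Mediated share (Section 5.1.3), for a linear model: S = 1 − adjusted gap / unadjusted gap = bG / (bG + U). Here b is the effect per unit of mediator, G the race gap in the mediator, and U the race gap left unexplained.

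Δ does not appear in S. S changes if G, U or b changes.

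**2. A small example**

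Take b = 0.1 outcome unit per mmHg and U = 1.2 units.

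- BP gap 8 mmHg: S = 0.8 / (0.8 + 1.2) = 40%.
- BP gap 4 mmHg: S = 0.4 / (0.4 + 1.2) = 25%.

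The share differs by 15 percentage points although every mmHg has the same effect in both cases. Section 5.1.3 reports that race differences in BP have increased over time. A gap widening from 4 to 8 mmHg would raise the share from 25% to 40%.

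**3. Four scenarios at three successive times**

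Inputs: race gap in exposure 0.5, effect 1 per unit in each period that matters, and U as listed. The simulation used 400,000 subjects and ordinary least squares. At each time the mediators are all exposures up to that time. Δ comes from the three-period model of Method 2: the first- and second-period coefficients added, for one unit high in both periods and normal in the third.

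| Scenario | Share by formula | Share simulated | Δ from period model |
|---|---|---|---|
| Reversible; U = 0.25, 0.25, 0.75 | 0.5/0.75 = 67%, 67%, 0.5/1.25 = 40% | 67%, 67%, 40% | 0.00 |
| Reversible; U = 0.25; exposure gap 0.50, 0.50, 0.15 | 67%, 67%, 0.15/0.40 = 37.5% | 67%, 67%, 37% | 0.00 |
| Irreversible; U = 0.25, 0.50, 0.75 | 0.5/0.75, 1.0/1.5, 1.5/2.25 = 67% each | 67%, 66%, 67% | 2.00 |
| Irreversible; no exposure gap; U = 0.25 | 0/0.25 = 0% each | about 0% each (0 to −2%) | 2.00 |

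The share drops in both reversible cases and is flat in both irreversible ones. A change in it is neither necessary nor sufficient for lost reversibility. The period model returns the true Δ in all four.

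**4. What the Objective 2 models cover**

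- Method 1 uses the total area. Ten high years followed by 20 normal years give the same area as 20 normal years followed by ten high, so it cannot isolate the earlier-high/later-normal group. It also looks for acceleration, which is a different question.
- Method 2, y = a + b₁X₁ + b₂X₂ + b₃X₃, holds later exposure fixed. Non-zero b₁ or b₂ is residual association after reduction, so Δ can be estimated.
- The third hazard model in Method 4 does the same on the log-hazard scale through time-specific weights.
- Both are additive across time as written. The residual from early exposure is the same whatever happens later, and no term lets the benefit of a later reduction depend on how long the factor was high. The duration part of Hypothesis 3 is therefore not tested.

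**The case against.** The best defence is that the sentence sits in the Objective 3 Summary, refers to the racial-disparity hypotheses, and says only that a point of no return will be suggested. It sets no threshold, test or decision rule. The Objective 2 hypotheses are called illustrative, further approaches are said to be under consideration, and the choice of model for each hypothesis is often left to an analysis plan, which is not shown.

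Much of this stands, and it limits the point. A reader might infer that Hypothesis 3 of Objective 2 is left with no valid test. The document does not support that: Objective 2 has its own methods, and the period model and the third hazard model can estimate past-exposure effects with later exposure held fixed. A reader might extend the equal-area objection to all the cumulative-exposure methods, but it applies only to total-area ones such as Method 1. A reader might also argue that the change of BP device at Y20 (Section 5.4) would itself shift the mediated share. A uniform shift leaves a race difference unchanged, and no race-differential error or change in precision is documented. Y20, Y25 and Y30 share one device.

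The defence does not rescue the inference itself. Hedged wording does not make the mediated share informative about reversibility, and no analysis plan can supply a link that the quantity lacks.

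**Conclusion.** The point holds in a limited form. The evidence that Section 5.1.3 names for a point of no return does not measure what Section 5.1.2 means by the term, and it can mislead in both directions. Separately, Objective 2 contains usable models but neither assigns one to Hypothesis 3 nor includes a term for its duration component.

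The logical conclusion follows from S = bG / (bG + U) and needs no particular parameter values. The sizes shown (67% to 40% or 37% with nothing irreversible; flat at about 67% or 0% with everything irreversible) rest on assumed gaps and effects in linear models without measurement error. They show that the failure is possible, not how large it would be in this cohort. The flaw is one of interpretation and specification. It affects no data collection and can be corrected before analysis.

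**What to change.** In the Section 5.1.3 Summary, delete the inference from a mediation change to a point of no return, or state that such a change describes race differences only.

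In Section 5.1.2, name the mutually adjusted three-period model as the analysis for Hypothesis 3. Report with confidence intervals the contrast of earlier-high/later-normal against persistently normal exposure at equal current level. Add an interaction between earlier duration elevated and later reduction, so that the duration component is tested. The third hazard model can serve the same purpose for event outcomes if given a corresponding term.

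The cost is a little extra analysis on repeated measures already held. Estimates will be imprecise where few participants were elevated for long and then controlled. Those who were controlled are partly selected by treatment, so the contrast remains an adjusted association and should be reported as one.
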